12.1. Pharmacokinetic Blood Sampling

Serial and fasting PK assessments will be performed in all patients participating in the study.

At Day 1, and Weeks 6, 12, 18, 24, 30, 36, and 48, patients will provide fasted blood samples for measurement of OCA and its conjugates, glyco-OCA and tauro-OCA, and metabolite OCA glucuronide 30 minutes before administration of investigational product (predose for ≥ 12 weeks) (Table 6). Patients will then receive a dose of investigational product with approximately 240 mL of water.

Week 6 Visit should occur 3, 4, or 5 days **after** the Week 6 dose (eg, if the Week 6 dose of investigational product is taken on a Sunday, the patient should come in for the Week 6 Visit between Wednesday and Friday [Figure 2]).

Figure 2: Week 6 Sampling Schedule

[figure not shown]

Week 6 Visit should be scheduled 3 to 5 days after the Week 6 OCA dose for collection of a single steady-state fasting PK sample

IP = investigational product; PK = pharmacokinetic

At Weeks 12, 18, 24, 30, and 48, serial PK blood samples will be obtained at 0.5, 0.75, 1, 1.5, 2, 2.5, 3, 4, 5, 6, 7, 8, 9, and 24 hours postdose (Figure 3) for all patients. The patient will be given the option to return to the clinic the following morning for the 24-hour postdose sample or samples can be obtained by a home health care designee. The home health care agency must be advised one week in advance of the appointment.

Figure 3: Pharmacokinetic Sampling Schedule

At meal timepoints, meals are consumed immediately after the collection of the PK sample

h = hour; IP = investigational product; PK = pharmacokinetic

Patients should not drink additional water for 1 hour after taking the dose of investigational product and will remain fasted until after the 1-hour sample is collected. A meal will be

provided following collection of the 1-, 4-, and 7-hour PK sample; the meal will be a meal replacement drink with nutrition information that has been submitted to and approved by the Sponsor in advance. No other food or drink (water is permitted) will be allowed until after the 7-hour sample collection.

During the treatment period:

- Pharmacokinetic fasting samples will be obtained from all patients at Weeks 6, 12, 18, 24, 30, 36, and 48 prior to dose administration in accordance with [Figure 3](#).
- Serial PK assessments will be performed in all patients at Weeks 12, 18, 24, 30, and 48.

Table 6: Acceptable Windows for Pharmacokinetic Sample Collection

Nominal Sampling Time	Acceptable Sampling Window
Before administration of investigational product (predose or fasting)	Within 30 minutes before dosing
0.5 to 1.5 hours after investigational product	± 10 minutes
2 to 2.5 hours after investigational product	± 20 minutes
3 to 24 hours after investigational product	± 30 minutes

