AE = adverse event; eCRF = electronic case report form; C4 = 7α hydroxy-4-cholesten-3-one; CK 18 M30 = cytokeratin-18 neopeptide M30; CLDQ = Chronic Liver Disease Questionnaire; ELF = enhanced liver fibrosis; ET = Early Termination; EOS = End of study; EOT = End of Treatment; ; FGF-19 = fibroblast growth factor-19; HA = hyaluronic acid; HCV = Hepatitis C virus; hs-CRP = high-sensitivity C-reactive protein; IL-6 = Interleukin 6; IP = Investigational Product; IgA = immunoglobulin A; IgG = immunoglobulin G; IgM = immunoglobulin M; P3NP = procollagen 3 N-terminal peptide; PBC = primary biliary cirrhosis; PK = pharmacokinetics; TE = transient elastography; wk(s) = week(s), TNF-α = tumor necrosis factor-α; TIMP-1 = tissue inhibitor of metalloproteinase ; VAS = Visual Analogue Scale.

^a Visit schedule should be based on Day 1. Day 1 visit must occur at least 2 weeks after screening visit.

^b Patients should be contacted by telephone/email every 3 weeks (±1 week) between clinic visits starting at Week 9 and continuing to Week 48 to assess for AEs, concomitant medications, medical/surgical procedures, and verify that s/he is dosing as directed. (see [Section 9.7.8](#)).

^c Preferably, the patient comes in to the clinic for this visit. Alternatively, site will telephone the patient for assessments and a home health nurse will visit to draw safety labs.

^d Visit should occur 3, 4, or 5 days after taking the Week 6 dose.

^e The patient should be instructed to fast overnight (at least 8 hours) prior to each visit. Fasting is required prior to all study visits, including screening, but water is permitted.

^f Height and assessment of smoking and alcohol consumption history and current habits will be assessed at Screening and Week 48. Assessment of smoking and alcohol consumption history and current habits will be assessed quarterly after Week 48.

- g Child-Pugh Score will be calculated based on ascites assessment, hepatic encephalopathy grade, and central laboratory evaluations per the Child-Pugh scoring system noted in the eCRF.
- h The EQ-5D-5L Quality of Life questionnaire is validated for use in multiple languages. If a validated translation is not available in the local language required for a specific study patient, the questionnaire will not be collected. The CLDQ measures change over time in patients with chronic liver disease.

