7.3. Planned Dosing Regimen

All patients will initiate investigational product once weekly with OCA 5 mg or matching placebo (Table 2). Titration may be considered as early as the Week 12 Visit. Following visit procedures at Week 12, if the investigational product is tolerated and laboratory assessments do not indicate a safety concern, the patient may up-titrate to OCA 5 mg twice weekly and may start the higher dose regimen no earlier than 2 days after they took their last dose. Dosing will then occur at least 3 days apart. Every 6 weeks thereafter, based on safety and tolerability assessments, patients can be considered for further up titration as described below (Table 2). At each titration visit, the patient may start the higher dose regimen no earlier than 2 days after the prior dose.

Patients with CP-B may titrate to a maximum dose of OCA 5 mg once daily.

Patients with CP-C may titrate to a maximum dose of OCA 10 mg twice weekly at least 3 days apart.

If, during the course of the study, a patient transitions from CP- B to CP-C, or vice versa, the maximal dose for the new CP classification would apply (Table 3).

Table 2: Planned OCA or Matching Placebo Dosing Regimen by Child-Pugh Score

	Child-Pugh B (Moderate Hepatic Impairment)		Child-Pugh C (Severe Hepatic Impairment)	
	Treatment Group		Treatment Group	
	OCA	Placebo	OCA	Placebo
Starting Dose (Day 1)	5 mg once weekly	matching placebo	5 mg once weekly	matching placebo
Titration 1^a	5 mg twice weekly ^b	matching placebo	5 mg twice weekly ^b	matching placebo
Titration 2^a	10 mg twice weekly ^b	matching placebo	10 mg twice weekly ^b	matching placebo
Titration 3^a	5 mg once daily	matching placebo	NA	NA

^a Planned titration regimen is shown; however, the titration of dose and/or frequency is dependent on patient tolerability and/or changes in Child-Pugh Score at any time during the study.

^b Dosing per the twice weekly schedule must be at least 3 days apart.

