9.7.6. Week 3 Safety Visit Procedures

Preferably, the patient will come in to the clinic for this visit. Alternatively, the site will telephone the patient for assessments and a home health nurse will visit to draw safety labs.

- Verify that patient is dosing as directed.
- Verify that the patient has fasted for at least 8 hours.
 - Record fasting status in the source and eCRF
 - If the patient reports having eaten within 8 hours, document accordingly in the source and eCRF and remind the patient that fasting is required prior to all study visits.
- Review and record prior concomitant medications.
- Assess and record AEs.
- Review and record any non-study related medical or surgical treatment procedures and any medically relevant HCP or non-HCP related office visits that have occurred since the previous study visit.
- Assess investigational product compliance, perform investigational product accountability.
- Obtain blood samples for
 - Serum chemistry, hematology, and coagulation
- Schedule the next visit (Week 6), reiterate dosing instructions, and advise the patient:
Week 6 Visit should occur 3, 4, or 5 days after taking the Week 6 dose, eg, if the Week 6 dose is taken on a Sunday, the patient should come in for the Week 6 Visit within the following Wednesday and Friday ([Figure 2](#)).
 - NOT to take investigational product on the morning of the next visit, and
 - To bring the investigational product bottle(s); s/he will dose at the clinic (if this is in compliance with the established dosing frequency), and
 - To fast overnight (at least 8 hours) prior to the next visit. Fasting is required prior to all study visits, but water is permitted.

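### Section 12.1 contradicts other protocol passages on whether investigational product is given at the Week 6 visit

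*Protocol*

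**What the plan says.** All references are to Protocol Version 2.

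**Text that ties the Week 6 sample to a dose (Section 12.1)**
- Week 6 is named in the visit list: "At Day 1, and Weeks 6, 12, 18, 24, 30, 36, and 48, patients will provide fasted blood samples".
- The sample is timed "30 minutes before administration of investigational product (predose for ≥ 12 weeks"), and the next sentence reads "Patients will then receive a dose of investigational product with approximately 240 mL of water".
- The closing bullet repeats the link: "Pharmacokinetic fasting samples will be obtained from all patients at Weeks 6, 12, 18, 24, 30, 36, and 48 prior to dose administration".
- Table 6 gives predose and fasting samples one shared window, defined relative to dosing. No other window is given for the Week 6 fasting sample.

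**Text that points the other way**
- Table 1 footnote d: "Visit should occur 3, 4, or 5 days after taking the Week 6 dose". Sections 9.7.6 and 12.1 say the same, and the note to Figure 2 describes the visit as 3 to 5 days after the "Week 6 OCA dose for collection of a single steady-state fasting PK sample".
- Section 7.3: "All patients will initiate investigational product once weekly with OCA 5 mg or matching placebo". Titration may be considered at the Week 12 visit at the earliest.
- Section 9.7.6, when booking the Week 6 visit: "s/he will dose at the clinic (if this is in compliance with the established dosing frequency").
- Section 9.7.7, the Week 6 procedures, has no administration step, whereas the serial PK visits have one (9.7.9 to 9.7.11).
- Table 1 shows no dispensing mark at Week 6.

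**The concern.** At Week 6 every patient is still on a once-weekly schedule. A visit placed 3 to 5 days after that week's dose cannot fall on a scheduled dosing day, so any dose given there is off schedule. Section 12.1 nevertheless describes one.

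The section is the operative text for PK visits, and PK is a primary objective. The patients are Child-Pugh B and C, for whom Section 5.4.2 predicts total OCA plasma concentrations 8.0 and 13 times those with normal hepatic function. Section 9.7.6 also asks patients to bring their bottle to the visit, so product would be on hand. Sites that resolve the conflict differently would dose differently during the once-weekly period.

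The dosing sentence also covers Week 36. Section 9.7.9 applies to Weeks 12, 24 and 36, but places its administration step under the serial PK assessment, which it limits to Weeks 12 and 24.

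**Working it through.** The protocol states no figure to reproduce here. The check is a calendar and a dose count.

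**Inputs**
- Once-weekly 5 mg from Day 1 (Section 7.3).
- Week 6 visit 3, 4 or 5 days after the Week 6 dose (Table 1 footnote d).
- Titration no earlier than the Week 12 visit; first step 5 mg twice weekly; twice-weekly doses at least 3 days apart (Section 7.3 and Table 2).
- Assumption: doses are taken exactly every 7 days, so dose day = 1 + 7k, and the Week 6 dose is k = 6.

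**Step 1: dates.** Week 6 dose: 1 + 7 × 6 = Day 43. Next weekly dose: Day 50. Week 12 visit: 1 + 7 × 12 = Day 85.

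**Step 2: spacing of a dose given at the visit**

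| Visit after Week 6 dose | Visit day | Days since last dose | Days to next dose |
|---|---|---|---|
| +3 days | 46 | 3 | 50 − 46 = 4 |
| +4 days | 47 | 4 | 50 − 47 = 3 |
| +5 days | 48 | 5 | 50 − 48 = 2 |

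The planned interval is 7 days. At +5 days the remaining gap of 2 days is below the 3-day minimum that the protocol sets for the twice-weekly regimen. The spacing depends only on the 7-day interval and the 3-to-5-day rule, not on which calendar day is called the Week 6 dose.

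**Step 3: load in that week (OCA arm).** Scheduled: 5 mg. With a visit dose: 5 + 5 = 10 mg. This equals the weekly total of the first titration step (2 × 5 mg), about 6 weeks before that step may be considered.

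**Step 4: load before the Week 12 visit.** Scheduled doses on Days 1, 8, …, 78: 12 doses, 12 × 5 = 60 mg. With one visit dose: 13 doses, 65 mg. Change: 65/60 − 1 = +8.3%.

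**Step 5: which reading do the passages support?** The dosing sentence, the closing bullet and the Table 6 window all attach a dose to the Week 6 sample. The visit timing, the frequency condition in 9.7.6, the silence of 9.7.7 and the predose qualifier in 12.1 detach it. No statement in the protocol says which governs.

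**The case against.** The strongest reply is that a careful reader can work out the answer. Section 12.1 labels the sample predose only from Week 12. The paragraph after the dosing sentence, and the note to Figure 2, describe Week 6 as a single steady-state sample. The condition in 9.7.6 fails under once-weekly dosing 3 to 5 days after a dose. Section 9.7.7 has no administration step, Table 1 has no Week 6 dispensing mark, and Section 9.1 speaks only of visits at which a dose is given at the site.

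This defeats two stronger inferences that a reader might draw.
- **That every patient would receive an extra dose.** That would require all sites to disregard the passages just listed. In the placebo arm, moreover, an extra tablet carries no OCA.
- **That the Week 6 PK result is spoiled.** The sample is drawn before any such dose. The next scheduled PK sample is at Week 12, with further weekly doses between, and the protocol passages at issue give no half-life from which to claim carry-over.

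The exposure argument also needs balance: Section 5.4.2 predicts liver increases of only 1.5- and 1.7-fold and reports no apparent effect on the overall safety profile. For Week 36, Section 9.7.10 gives the same frequency condition when the next visit is booked after Week 30.

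What remains is the contradiction. The predose qualifier labels the sample; it does not limit the dosing sentence that follows. The closing bullet names Week 6 with no qualifier at all. The mitigating passages are the other half of the conflict and do not resolve it.

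**Conclusion.** The protocol contradicts itself on whether product is given at the Week 6 visit. It supports an inconsistency that some sites could act on, not a certain extra dose for all patients.

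On the literal reading of 12.1 the size for an OCA patient is one 5 mg tablet: a doubled load in one week and 8.3% more over the first 12 weeks, given before titration may first be considered. On the other reading it is zero. The figures assume exact 7-day dosing and full compliance. How many sites would read it either way cannot be derived from the document.

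The cumulative effect is small. The point still merits correction, because it concerns an operative dosing instruction in patients with moderate to severe hepatic impairment and could make dosing differ between sites. Week 36 shows a related but weaker mismatch between 12.1 and 9.7.9. A likely origin is incomplete revision: Version 1 of the protocol has the same dosing sentence after a predose sample at each visit, and Version 2 moved the Week 6 visit to mid-interval but kept it.

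**What to change.** Reconcile Section 12.1 (the dosing sentence, the closing bullet and the Table 6 window) with Table 1 footnote d, Sections 9.7.6, 9.7.7 and 9.7.9, and Figure 2. The protocol should state, in the same terms in each place, at which visits product is given in clinic and how the Week 6 and Week 36 samples relate to dosing. Which visits carry a dose is for the sponsor to settle; this review does not choose.

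The cost is a wording change in the protocol and in any site PK instructions drawn from it. It adds no visit, sample or patient and leaves the analysis unchanged.

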5.3. Clinical Development of Obeticholic Acid

As of 31 Jan 2017, approximately 2186 patients have received at least 1 dose of OCA. Of these, 844 were healthy volunteers, 525 patients had PBC, 686 patients had nonalcoholic steatohepatitis (NASH), 41 patients had diabetes mellitus/ nonalcoholic fatty liver disease (NAFLD), 33 patients had alcoholic cirrhosis/portal hypertension, 52 patients had primary sclerosing cholangitis (PSC), and 5 patients had biliary atresia.

Overall, the pharmacokinetic (PK) profile of OCA is consistent with that expected of a bile acid. Phase 1 studies demonstrated that OCA is rapidly absorbed and extensively conjugated with glycine and taurine to form glyco-OCA and tauro-OCA, respectively. OCA and its conjugates are primarily eliminated via biliary excretion, and plasma concentration time profiles demonstrated multiple peaking with prolonged exposure, indicative of enterohepatic circulation.

Plasma concentrations of OCA and its conjugates spike shortly after meals, consistent with gall bladder emptying into the duodenum as expected of a bile acid.

The OCA clinical development PBC program was based on a wide range of studies in PBC patients and healthy volunteers. The clinical pharmacology studies supported the proposed dosing regimen: 10 mg fixed dose and a titration regimen starting at OCA 5 mg with titration to 10 mg based on clinical and biochemical response. The clinical program included a pivotal Phase 3 clinical study (747-301) and two Phase 2 clinical studies (747-201 and 747-202), which formed the primary basis of approval of OCA.

Study 747-201 (59 patients) evaluated 2 doses of OCA (10 mg and 50 mg) given as monotherapy versus placebo. Statistically significant and clinically relevant relative and absolute reductions from Baseline in alkaline phosphatase (ALP) were achieved with both doses of OCA versus placebo ($p < 0.0001$). Mean relative ALP reductions were 45% (OCA 10 mg) and 38% (OCA 50 mg) compared to an increase of 0.4% with placebo. Further, significant improvements in gamma-glutamyl transferase (GGT) and in conjugated bilirubin were observed with both doses compared with placebo ($p < 0.05$). OCA also resulted in decreased circulating alanine aminotransferase (ALT) and aspartate aminotransferase (AST) levels.

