15.3. Pharmacokinetic Analyses

The PK Population will be used for analysis of PK parameters, which include plasma OCA (parent) and its conjugates (glyco-OCA and tauro-OCA), total OCA, metabolite OCA glucuronide, and potentially other conjugates or metabolites not yet identified.

PK analysis will be based on the PK population. Values will be calculated using non-compartmental methods. The values will be summarized by active treatment group using descriptive statistics.

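### Serial PK ends at 24 h on every regimen and Section 15.3 pools regimens in one OCA group; summarize PK by regimen and on average exposure

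*Protocol*

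**What the plan says.** Section 12.1 sets the serial times: "serial PK blood samples will be obtained at 0.5, 0.75, 1, 1.5, 2, 2.5, 3, 4, 5, 6, 7, 8, 9, and 24 hours postdose". The same grid applies whatever the regimen: "Serial PK assessments will be performed in all patients at Weeks 12, 18, 24, 30, and 48".

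Section 7.3 lets the dosing interval vary. At the start, "All patients will initiate investigational product once weekly with OCA 5 mg or matching placebo". Titrations 1 and 2 are 5 mg and then 10 mg twice weekly, with the condition that "Dosing per the twice weekly schedule must be at least 3 days apart". For Child-Pugh B there is a further step: "Patients with CP-B may titrate to a maximum dose of OCA 5 mg once daily".

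Section 15.3 fixes the analysis: "Values will be calculated using non-compartmental methods", and "The values will be summarized by active treatment group using descriptive statistics". Section 9.1 has only two groups, OCA and placebo, so there is one active group. Section 15.3 names no exposure parameter and no interval for it.

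Two other kinds of sample bear on the rest of the interval. Section 12.1 takes a fasting predose sample at each serial visit, and one sample 3 to 5 days after the Week 6 dose. Section 5.3 describes the profiles of OCA and its conjugates as having "demonstrated multiple peaking with prolonged exposure, indicative of enterohepatic circulation". It gives no half-life.

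**The concern.** A 24-h profile is a whole dosing interval only for a patient on daily dosing. On weekly dosing it leaves out six of seven days, and on twice-weekly dosing about two and a half of three and a half. The protocol itself describes exposure as prolonged. A non-compartmental AUC to the last sample therefore means something different on each regimen.

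The grouping compounds this. Titration follows the Week 12 procedures, so the Week 12 profile should be on weekly dosing for nearly everyone. From Week 18 regimens can differ between patients. With titration at every opportunity (Weeks 12, 18 and 24), a Child-Pugh B patient can be on daily dosing at Weeks 30 and 48, while a Child-Pugh C patient stays at no more than 10 mg twice weekly. A summary of the OCA arm at those visits then mixes full-interval and part-interval values, and weekly doses that can differ up to sevenfold.

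PK is a primary objective (Section 6.1), PK parameters feed the PK/PD objective (Section 6.3), and the dose rationale in Section 5.4.2 is argued on steady-state exposure. A summary that does not separate regimens is hard to use for any of these.

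**Working it through.** The protocol states no coverage figure, so there is none to reproduce.

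**Inputs.** Last serial sample 24 h (Section 12.1). Dosing interval τ: 168 h weekly; twice weekly 84 h on average, or 72 h and 96 h in a fixed weekly pattern with at least 3 days between doses; 24 h daily (Section 7.3). Weekly dose: 5, 2 × 5 = 10, 2 × 10 = 20 and 7 × 5 = 35 mg. Half-life: not given, so assumed over 4 to 168 h.

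**Coverage = 24/τ.** Weekly 24/168 = 14.3%. Twice weekly 24/84 = 28.6% (24/96 = 25.0%, 24/72 = 33.3%). Daily 24/24 = 100%.

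**What AUC0-24 measures.** Assume steady state, linear kinetics, equal clearance and mono-exponential decline with k = ln 2 / half-life. Then AUC0-24 is proportional to D(1 − e^(−24k)) / (1 − e^(−kτ)), with D the dose per administration. Average concentration is proportional to D/τ, hence to weekly dose: 5:10:20:35 = 1:2:4:7. The (D, τ) pairs are (5, 168), (5, 84), (10, 84) and (5, 24).

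| Assumed half-life | AUC0-24 over the four regimens | 5 mg daily ÷ 10 mg twice weekly |
|---|---|---|
| 4 h | 1 : 1.00 : 2.00 : 1.02 | 0.51 |
| 12 h | 1 : 1.01 : 2.02 : 1.33 | 0.66 |
| 24 h | 1 : 1.09 : 2.18 : 1.98 | 0.91 |
| 48 h | 1 : 1.30 : 2.59 : 3.11 | 1.20 |
| 96 h | 1 : 1.55 : 3.09 : 4.42 | 1.43 |
| 168 h | 1 : 1.71 : 3.41 : 5.30 | 1.55 |
| Average concentration | 1 : 2 : 4 : 7 | 1.75 |

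No row matches the last one. AUC0-24 approaches 1:2:4:7 only as the half-life becomes very long relative to a week.

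**How much is truncation and how much is dosing frequency.** A fully sampled AUC over τ is proportional to dose per administration and would read 5:5:10:5 = 1:1:2:1. Truncation alone is seen in AUC0-24 as a share of AUC over τ (weekly / twice weekly / daily): 0.98/0.98/1.00 at 4 h, 0.75/0.76/1.00 at 12 h, 0.50/0.55/1.00 at 24 h, 0.32/0.42/1.00 at 48 h and 0.23/0.35/1.00 at 96 h. Truncation is thus negligible at a short half-life and large at a long one. In either case a per-dose value must be converted to a common time base before regimens are compared.

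**Can the samples already planned supply the full interval?** At steady state the predose value at a serial visit stands for the end-of-interval concentration. Under the same model, log-linear interpolation from 24 h to predose recovers 100% of AUC over τ. That is true by construction and says nothing about meal-driven peaks. Linear interpolation overstates it:

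| Assumed half-life | Weekly, linear | Weekly, linear, with a Week 6 point at 96 h | Twice weekly, linear |
|---|---|---|---|
| 12 h | +79% | +29% | +21% |
| 24 h | +57% | +17% | +11% |
| 48 h | +23% | +6% | +4% |
| 96 h | +7% | +2% | +1% |

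The interpolation rule therefore matters and should be fixed in advance.

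**The case against.** The best reply is that Section 15.3 promises only descriptive non-compartmental values. It names neither AUC0-24 nor a comparison across regimens, and the choice of parameters and interpolation rules is ordinary SAP content. This stands for the parameter names, and their absence is not held against the protocol. It does not cover the two things the protocol does fix: one 24-h grid for every regimen, and a summary by active treatment group when there is only one such group.

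A second reply is that the sampling was thought through. The summary of changes says times were added to characterize steady state on the less frequent regimens, and Section 12.1 provides the predose and Week 6 samples. This also stands, and it is why no further sampling is requested. The limits are that twice-weekly dosing has nothing between 24 h and the next predose sample, and that the Week 6 sample serves weekly dosing only and comes from a different interval.

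A reader might infer three stronger conclusions that the documents do not support:

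- **That the 24-h stop itself makes 5 mg daily appear below 10 mg twice weekly.** It does not. That ordering appears for half-lives under about 30 h because AUC0-24 ignores dosing frequency. A fully sampled per-interval AUC would give a ratio of 0.50. Multiplying AUC0-24 by doses per week errs the other way: 35/(20 × 0.756) = 2.3 at 12 h and 35/(20 × 0.350) = 5.0 at 96 h, against 1.75.
- **That the primary objective is exposure at each titration step.** Section 6.1 speaks of evaluating the PK of OCA and its conjugates, with no titration-step or Child-Pugh contrast.
- **That the results would give false reassurance about the Child-Pugh B maximum.** Section 5.4.2 rests that maximum on prior estimates, and nothing says this trial's AUC will be used to justify it.

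**Conclusion.** The point holds as a matter of summary and labelling, not as a failure of sampling. Followed as written, Sections 12.1 and 15.3 give values that observe 14%, about 29% or 100% of the interval and are pooled over regimens of 5 to 35 mg per week. AUC0-24 from this grid does not track average exposure across regimens at any half-life tried between 4 and 168 h. Cmax and predose concentration remain usable at every step.

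The coverage percentages follow directly from the protocol. The exposure ratios rest on assumed half-lives, linear kinetics, equal clearance and mono-exponential decline, and the last of these is a simplification given the multiple peaks in Section 5.3. The ratios show the size of the problem and do not predict results. The change is inexpensive and worth making because PK is a primary objective.

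**What to change.** In Section 15.3:

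1. Summarize PK by the regimen in use at the visit and by Child-Pugh class, not only by active treatment group.
2. Compare regimens on average concentration or weekly AUC. Obtain it by log-linear (not linear) interpolation from the 24-h sample to the same visit's predose value, taken as the end-of-interval concentration at steady state. Use recorded dose times, since twice-weekly intervals may be 72 or 96 h. The alternative is a population PK model of all fasting and serial samples, including Week 6.
3. Label AUC0-24 as dosing-day exposure and do not rank regimens on it.

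The cost is analysis wording and, if the second route is taken, some modelling. No samples, visits or doses change. The downside is that the stretch from 24 h to predose rests on few points and does not capture meal-driven peaks, so the results should state that this part is interpolated.
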